The study was designed to enroll 75 subjects with an expectation anticipating 25% loss to follow-up with an anticipated of n=66 subjects completing the study. The study ultimately recruited 74 subjects with 66 subjects completing the study. As this study was initiated prior and enrolled through the COVID-19 pandemic, subjects' follow-up times extended beyond 24 weeks; this modification was approved by the Mass General Brigham Institutional Review Board. All patients were enrolled from rheumatology practices at Brigham and Women's Hospital, Brigham and Women's Faulkner Hospital, Massachusetts General Hospital, Boston, MA and Mount Auburn Hospital, Cambridge, MA. All PET MPI was performed at Brigham and Women's Hospital.

Study Outcomes and Measures

The primary outcome was the change in global MFR after 24 weeks of treatment starting with TNFi therapy. MFR, the ratio of peak vasodilator stress to rest MBF, represents the maximal ability to augment coronary flow and myocardial perfusion. The secondary outcome was change in hs-cTnT at baseline and 24 weeks. Inflammatory marker and hs-cTnT measurement was also available for baseline, week 6, 12 and 24 weeks.

Inflammatory biomarkers

Blood biomarkers were measured and broadly categorized into clinically measured acute phase reactants and inflammatory pathways implicated in RA or CVD. The acute phase reactants included: erythrocyte sedimentation rate (ESR) and high sensitivity C-reactive protein (hsCRP), measured using clinical assays. The remainder of the biomarkers were measured at Children's Hospital as previously described. Inflammatory pathways implicated in RA or CVD comprised of IL-1a, IL-1b, IL-6, and sTNFR2. Inflammatory biomarkers without clinical cut-off values were categorized into tertiles. Changes in biomarkers were also categorized into tertiles.

Clinical measurements

RA Disease Activity was assessed using the validated disease activity score (DAS)28-CRP with 3 components. DAS28-CRP3 incorporates the 28 tender and swollen joint count and hsCRP. We additionally calculated the clinical disease activity index (CDAI), which does not include hsCRP in the calculation.

Statistical Analysis

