Means and standard deviations were used to describe most continuous variables, medians and IQRs were used to describe variables with non-normal distributions, and frequency and percent were used to describe categorical variables. Comparison p-values for outcome variables and other variables before and after TNFi therapy were computed using paired t-tests or the Wilcoxon signed rank test for non-normally distributed variables. Spearman's correlation was used to test the correlation between the log of baseline inflammatory markers and the primary outcome, MFR, and secondary outcome, hs-cTnT. As well, Spearman's correlation was used to test the relationship between change in inflammation and the primary and secondary outcomes. An exploratory subgroup analysis was also performed to test the correlation between change in inflammatory markers with change in hs-cTnT, among subjects with CMD (MFR<2.5) at baseline and 24 weeks. As measurements were available for inflammatory markers and hs-cTnT at

multiple time points, we additionally tested the association between the inflammatory markers with hs-cTnT over time.

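### Is it a defect that inflammation is related to MFR only by unadjusted Spearman correlations, with no slope or confidence interval?

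*Combined protocol and SAP*

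**What the plan says.** Study Outcomes and Measures defines the endpoint: "The primary outcome was the change in global MFR after 24 weeks of treatment starting with TNFi therapy". The Statistical Analysis section tests that change with p-values "computed using paired t-tests or the Wilcoxon signed rank test for non-normally distributed variables".

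The link with inflammation is a separate question, addressed in two ways. For baseline values, Spearman's "correlation was used to test the correlation between the log of baseline inflammatory markers and the primary outcome, MFR". For changes, Spearman's "correlation was used to test the relationship between change in inflammation and the primary and secondary outcomes". Neither sentence names a covariate, a slope or an interval.

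Three further statements bear on the point:

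- Inflammatory biomarkers: "Changes in biomarkers were also categorized into tertiles". The Statistical Analysis section names no test that uses these groups.
- Effect of reducing inflammation on CMD, primary cohort: because of the pandemic, "follow-up times extended beyond 24 weeks".
- Statistical Analysis, last sentence: "we additionally tested the association between the inflammatory markers with hs-cTnT over time". MFR is not mentioned there.

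**The concern.** The study has no concurrent untreated or randomised arm; the healthy controls serve only the baseline imaging comparison. A correlation between marker change and MFR change is therefore observational. Patients entered with active disease, so the markers may regress to the mean. The interval between scans varied and could affect both changes. If baseline marker and baseline MFR are related, or a third factor drives both changes, a significant rho could arise with no direct link. A p-value without an interval would also hide how imprecise 66 patients leave the estimate.

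These correlations are the only stated tests of whether a fall in inflammation goes with a rise in MFR, so that reading is what is at stake. The obvious candidate remedy is a regression of 24-week MFR on change in log marker, adjusted for baseline marker, baseline MFR, age, sex and weeks between scans. The question is whether leaving it out is a fault.

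**Working it through.** **1. What the stated sample size implies.** Inputs: 66 completers (Effect of reducing inflammation on CMD, primary cohort) and two-sided 0.05 (assumed; the plan gives no alpha).

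- Critical value: tanh(1.96/√(66−3)) = tanh(0.247) = 0.242.
- 95% interval: tanh(atanh(rho) ± 1.96·√((1+rho²/2)/(n−3))).
- At rho = −0.25: atanh = −0.2554, SE = √(1.03125/63) = 0.1279, so the limits are tanh(−0.506) and tanh(−0.005), or −0.47 to −0.005.
- At rho = −0.35: −0.55 to −0.11.

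The interval needs only rho and n. A reader given rho can compute it, so its absence from a short methods text conceals nothing.

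**2. Regression to the mean.** Assume no link, retest correlations rx (marker, 0.4–0.6) and rm (MFR, 0.4–0.7), and baseline correlation r0. The documents give none of these. If each follow-up value depends only on its own baseline plus independent noise, the correlation of the two changes is r0·√((1−rx)(1−rm))/2.

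- At r0 = −0.3 this is −0.3·√(0.6·0.6)/2 = −0.090 at most and −0.3·√(0.4·0.3)/2 = −0.052 at least.
- Against the critical value of 0.242, that is a modest bias.
- The model also implies a follow-up correlation of rx·rm·r0, here 0.4·0.4·(−0.3) = −0.05 to 0.6·0.7·(−0.3) = −0.13. The baseline association must fade by more than half for the bias to appear.

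If the cross-sectional association instead comes from stable traits measured with noise, the changes contain only the independent noise. Spearman is then unbiased, and the regression picks up the trait correlation.

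**3. Common cause.** Let an unmeasured factor act on the follow-up residuals and correlate a with marker change and −a with MFR change. The raw correlation of changes is −a². Conditioning on both baselines removes variation unrelated to the factor, so the partial correlation becomes −2a²/√((1+rx)(1+rm)). With a = 0.3 and rx = rm = 0.5, this is −0.18/1.5 = −0.12, against −0.09 unadjusted. For any retest correlation below 1, the adjusted analysis is more affected than the unadjusted one.

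**4. False-positive rates by simulation, n = 66, no true link.** The regression is the seven-parameter model described above (59 residual degrees of freedom).

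| Assumed situation | Spearman | Adjusted regression |
|---|---|---|
| Baselines regress, r0 = 0 | 4.2–5.4% | 4.3–5.5% |
| Baselines regress, r0 = −0.2 | 4.9–7.2% | 4.4–5.4% |
| Baselines regress, r0 = −0.3 | 6.7–10.4% | 4.5–5.6% |
| Stable traits correlated −0.2 | 4.8–5.2% | 5.0–6.0% |
| Stable traits correlated −0.5 | 4.5–5.3% | 8.9–10.7% |
| Unmeasured common cause, a = 0.2 | 5.8–6.0% | 6.2–7.2% |
| Unmeasured common cause, a = 0.3 | 10.1–10.9% | 13.9–16.8% |
| Unmeasured common cause, a = 0.4 | 22.5–22.8% | 31.3–43.1% |

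The first five rows use 5,000 trials per cell and the last three use 3,000. The simulation standard error near 10% is √(0.1·0.9/5000) = 0.4 points, or √(0.1·0.9/3000) = 0.5 points.

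A regression holds its level against a common cause (4.9–5.0%) only when that cause is itself in the model. The proposed covariates help only if the cause is age, sex or weeks between scans. Change scores already remove age and sex effects that are additive and constant over time.

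**5. The over-time analysis.** Study population and design places PET imaging at baseline and at the 24-week visit only. Markers and hs-cTnT were also measured at weeks 6 and 12. With two MFR values per patient, the change in MFR already is the over-time measure, so restricting the repeated-measures analysis to hs-cTnT follows from the data.

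**The case for a change.** The strongest case for the concern is that the Objective speaks of the relative contribution of inflammation and lipids, which pairwise correlations cannot deliver, and that one regression per marker on data already collected costs little.

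The first part is true, but the adjusted regression contains no lipid term, so it would not serve that aim either. On cost, the plan lists hsCRP and ESR plus four others ("Inflammatory pathways implicated in RA or CVD comprised of IL-1a, IL-1b, IL-6, and sTNFR2"), which makes six post hoc models. Even on the concern's own terms, they would neither replace the Spearman test nor decide any claim.

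Some of it stands. Printing an interval beside rho is good reporting practice. If scan interval did relate to both changes, adjusting for it would help, but the plan does not give the spread of intervals or any such relation. The tertiles of biomarker change are left without a named analysis; that is a loose end, and it does not affect the correlations. A significant rho should be read as association in an uncontrolled cohort. The plan's wording, which speaks of correlation and relationship, does not claim more for these tests.

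**Conclusion.** The concern does not hold. It is correct that the plan names no slope, interval or adjusted model for MFR. But Spearman correlation is a valid test of association, the paired analysis of the primary outcome does not depend on it, and nothing as written is shown to give a wrong result.

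The suggested regression protects in one assumed situation (4.5–5.6% against 6.7–10.4% at r0 = −0.3). It does worse in two others (8.9–10.7% against 4.5–5.3% with stable traits correlated −0.5; 13.9–16.8% against 10.1–10.9% with an unmeasured common cause at a = 0.3). All of these rates rest on assumed baseline, retest and common-cause correlations. Because the documents give none of them, neither analysis can be called better. What is left is a preference about reporting, since the interval for rho can be computed from rho and n = 66.
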